**UNIVERSIDADE FEDERAL DE SANTA CATARINA
CAMPUS ARARANGUÁ-ARA**

[name]
[contact] / [name]

RESEARCH PROJECT

Dry Needling and Photobiomodulation in the treatment of Myofascial Pain

Study Principal Investigator: [name] [name].

ABSTRACT

Myofascial Pain is a clinical condition of myalgic pain characterized mainly by the presence of Myofascial Trigger Points. Trigger points can be active or latent and they are described as a hypersensitive spot within a taut band in the muscle. The use of a computer for long periods has been shown as a trigger the trigger points. Dry Needling and Low-Level Laser Therapy (LLLT) has been described as good resources to treat myofascial pain. The hypothesis is that the association of the purposed interventions will have greater effects than only the dry needling intervention. The objective is to evaluate the effects of the dry needling and the laser in the treatment of upper trapezius trigger point on women. This study is composed of an evaluation and an intervention proposal with dry needling and LLLT to treat myofascial trigger points. The sample will be composed of 60 women, with 18 to 65 years old, divided into three groups. Twenty individuals will be in group Dry-On that will receive dry needling intervention on the trigger point, followed by LLLT intervention on. Twenty individuals will be in group Dry-Off that will receive dry needling intervention on the trigger point, followed by LLLT intervention turned off. Twenty individuals will be in group Control that will receive dry needling intervention at 1.5 cm from the trigger point, followed by LLLT intervention turned off. All interventions will be performed in one session. Outcome measures for pain, pressure pain threshold, functionality, and muscle activity will be collected.

Key-words: Myofascial pain; Pressure Pain Threshold; Low-Level Laser Therapy; Dry needling;

1. INTRODUCTION

The International Association for the Study of Pain (IASP) defines pain as “an unpleasant sensory and emotional experience associated with actual or potential tissue damage, or described in terms of such damage” (1). The Myofascial Pain is the clinical condition where the patient presents regional muscle pain, and that is characterized by the presence of symptomatic trigger points in one or more sites, which can be associated to local or referred pain, muscle spasms, increase in sensibility, stiffness, muscle weakness, decrease in range of motion, and autonomic dysfunction (2,3).

Women are the most affected by myofascial pain. It may be explained once women have lower pain pressure threshold (PPT) compared to men, which means higher hypersensitivity to mechanical stimulation (4). Moreover, both gender also has differences in electromyographic findings when induced to muscle pain, suggesting that women have a mechanism of protector adaptation less efficient to pain stimulation than men’s protector mechanism (5).

According to Simons & Travell (6), the myofascial trigger point is a hyperirritable spot, hypersensitive nodule palpable inside of a tender band that is painful on compression and that can give rise to referred pain, tenderness, and autonomic phenomena. This palpable nodule is usually located in hyperalgesic areas inside muscle, ligaments, and tendons, and it is associated with several conditions of chronic pain (2,7,8). The trigger points are classified as active and latent, where active trigger points have spontaneous local pain and referred pain away from the trigger point spot. The latent trigger point demonstrates pain only when stimulated with mechanical pressure, what can evoke local and/or referred pain without spontaneous pain (7).

Several studies have shown a variety of therapeutic resources that can be used in the treatment of trigger points and the myofascial pain, as: lidocaine injection (3,9), exercise and stretching (10), dry needling (7,11,12), photobiomodulation (13), therapeutic ultrasound (14,15) and ischemic compression (16).

The dry needling technic has been growing and gaining space among physical therapists as an option to treat myofascial pain and trigger points (7). The technic is described as an intervention where a fine, solid and filiform needle is inserted through the skin to stimulate trigger points, muscle and connective tissue to modulate neuromusculoskeletal pain and movement limitation (2,17). One mode of dry needling application is the fast-in and fast-out

technique developed by Hong, which consists in moving the needle up and down during approximately 30 seconds or until the local twitch response disappears (9,18).

Clinical trials using the dry needling technique in trigger points on upper and lower trapezius demonstrate improvement in pain, increase of PPT and on neck pain questionnaires scores, and an increase of cervical range of motion (ROM) compared with groups where the dry needling was applied away from the trigger point or that do not receive intervention (19,20). Espejo-Antúnez et al (12), in 2017, concluded in their systematic review that the dry needling can result in positive effects at short-term on pain, the range of motion, and quality of life when compared to placebo groups or groups without intervention; and it has similar effects to pharmacological intervention.

Photobiomodulation resources, like Low-Level Laser Therapy (LLLT), have been studied as a resource to treat trigger points and myofascial pain. Ilbuldu et al (13), in 2004, verified that the LLLT has an effect on the treatment of upper trapezius trigger point by decreasing pain, increasing pain pressure threshold, increasing the cervical range of motion, and improving functional activities before 4 weeks of intervention. The treatment was performed 3 times per week for 4 weeks and used a He-Ne laser equipment, 632.8 nm, 2J of energy. Uemoto et al. (21), in 2013, used a dose of 4 J/cm²m wavelength of 795nm, 80mW, on masseter trigger points and they find positive results to inhibit trigger point, improve pain and increase PPT.

These effects can be explained on the red light spectrum, near to infrared (660nm-905nm), have good effects to reduce inflammation, relieve pain, and accelerate the tissue regeneration (22). According to Gerwin (4), 2010, the LLLT has level B of the recommendation of probable effect on the treatment of pain caused by myofascial trigger points. Gattie et al (23), 2017, in their systematic review, state that the current information on dry needling intervention, whether compared to placebo treatment or when compared to another intervention, has very low to moderate quality of evidence. Furthermore, although the trigger points demonstrate changes in muscle activation obtained through electromyography (EMG), there are few studies that present EMG findings in order to demonstrate the effects of dry needling directly on muscle activity (24,25)

In this context, the present study aims to answer if the association of dry needling and photobiomodulation will have a greater effect on the treatment of myofascial trigger points than the dry needling alone or the placebo treatment.

2. OBJECTIVES

2.1. General Objective

The present study has the objective to evaluate the effects of dry needling and photobiomodulation application in the treatment of trigger points in upper trapezius on women with myofascial pain.

2.2. Specific Objectives

To evaluate the pain level before, during, and after the dry needling and photobiomodulation applications on the trigger point.

To identify the pain pressure threshold before and after dry needling and photobiomodulation applications on the trigger point

To verify the electromyographic activity of upper trapezius before and after the proposed treatments

To compare the effects fond intra and inter-groups for the applications of dry needling, dry needling and photobiomodulation, and control protocol.

3. METHODS

3.1. Study Design

The present study is characterized as a randomized clinical trial, controlled, with a proposal of evaluation and intervention of dry needling associated to the low-level laser therapy (LLLT) to treat the trigger point caused by myofascial pain. The subjects will be randomized into three groups:

- Group On: application of dry needling and LLLT turned on directly on the trigger point;
- Group Off: application of dry needling and LLLT turned off directly on the trigger point;
- Placebo/Control group: application of dry needling and LLLT turned off away from the trigger point.

3.2. Local of the Study

The study will be performed at the Laboratory of Evaluation and Rehabilitation of the Locomotor Apparatus (LARAL), located at Universidade Federal de Santa Catarina, Campus Araranguá, Santa Catarina, Brazil.

3.3. Subjects

Women, with age between 18 and 65 years old, students, workers, and professors at Universidade Federal de Santa Catarina (UFSC) will be invited to participate in the research.

The invitation of subjects to participate in the study will be done through digital and printed folders that will be delivered at UFSC and on the social media. Those subjects that show interest to participate will be forwarded to an evaluation selection where it will be identified if the participant fits the inclusion criteria and where the Consent Form will be presented.

The sample will be composed by 20 subjects in each group, a total of 60 subjects, according to a convenience sample based on review studies of Cagnie et al., 2015(26), and Espejo-Antúnez et al., 2017 (12).

3.3.1. Inclusion Criteria

- Presence of active trigger point in upper trapezius.
- Use of computer for typing activities for, at least, 20 hours per week.
- Presence of mechanic pain in cervical region for less than three months.
- Pain level higher than 3 and lower than 8 on the Visual Analogue Scale (VAS) for neck and cervical regions in the last 30 days.

3.3.2. Exclusion Criteria

- Body Mass Index (BMI) higher than 30
- Presence of whiplash injury or other cervical pathologies such as herniated disc and Thoracic Gorge Syndrome;
- Presence of contraindication to the treatment with low-level laser therapy or with dry needling
- Fear of needles
- To be receiving treatment for the pain in neck and/or shoulder regions
- Make use of analgesic drugs, anti-inflammatory and/or muscle relaxants and anticoagulant medications.

3.4. Evaluation procedures

The active trigger point in upper trapezius will be localized through manual palpation and the location will be marked with a special pen for the skin. A second mark located 1.5 centimeters medially from the trigger point will be made in all subjects. The trigger point identification will follow Simons et al. (6,27) criteria, featuring 3 of 4 items: (1) presence of

palpable taut band in the muscle; (2) presence of hypersensitive spot inside the taut band; (3) subject recognize the familiar pain; and (4) painful limitation of the range of motion during total stretch.

The surface electromyography (EMG) will be used to evaluate the muscle recruitment pattern. It will be used the equipment Miotec® (Miotool 400, Software Miograph®), with analog to digital (A/D) converter of 14 bits of resolution, amplified acquisition in 2000 Hz, common rejection mode of 100 dB, and band-pass filter set between 10-500 Hz. Disposable electrodes, made with polyethylene foam and with hypoallergenic adhesive, solid gel adherent, bipolar contact of Ag/AgCl (silver/silver chloride), will be used and positioned with 20mm of distance between poles. The Medtrace® reference electrode will be positioned in the ipsilateral wrist of the data collection. The electrodes will be positioned in the upper trapezius muscle as recommended by SENIAM (Surface ElectroMyoGraphy for the Non-Invasive Assessment of Muscles).

The skin where the electrodes will be positioned will be prepared according to SENIAM recommendation. It will be performed the removal of local hairs with the aid of a disposable razor and the skin will be slight exfoliated with dermatological sandpaper. The process of skin preparation will be finished with the use of a cotton moistened with 70% alcohol on the site with the purpose of reducing the electrical impedance of the skin for the posterior capture of EMG signals (28). The subject will be asked to perform a shoulder abduction of 90°, without additional load and with the hand facing down, and maintain this position for 15 seconds. This movement will be repeated four times, with 30 seconds of rest interval (24,29). For data analysis will be used the Root Mean Square (RMS) and Medium Frequency (FMed) data in microvolts and Hertz, respectively.

The Visual Analogue Scale (VAS) will be used so the subjects can graduate their pain in shoulder and neck regions. The VAS level of pain will be acquired before the intervention (baseline), soon after the intervention (T₁), 30 minutes after the intervention (T₂), one week (T₃) and one month (T₄) after the intervention.

Pressure algometry will be used to evaluate the pain pressure threshold (PPT). This measured will be obtained before the intervention (baseline), soon after the intervention (T₁), and 30 minutes after the intervention (T₂). The equipment will be positioned on the trigger point mark and the subject will be instructed to report when the sensation changes from pressure to pain (16). The force measured in kilograms per square centimeter (kg / cm²) will correspond to

the quantity of pressure needed so the subject report change in pressure pain sensation (14). The pressure will increase constantly on 1 kg / cm² / s. It will be collected three measured, with an interval of 20 seconds between each measure, and the average of the three values will be used in data analysis.

The Neck Disability Index (NDI) is a unidimensional questionnaire composed of 10 items that have the aim to evaluate the limitation caused by pain and disability on the neck (30). This questionnaire is organized according to the type of activity performed and express positive levels of functional capability. Its score ranges from 0 to 50, where 0 to 4 is considered total capacity, 5 to 14 is mild incapacity, 15 to 24 is moderate incapacity, 25 to 34 is serious incapacity, and >35 is severe incapacity. The questionnaire will be self-applied and the subject will answer it before the intervention, one week and one month after intervention.

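### Does the 3-of-4 identification rule leave the required active status of the trigger point unverified?

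*Combined protocol and SAP*

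**What the plan says.** Four parts of the combined protocol and SAP bear on this.

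- **Eligibility.** The first inclusion criterion in section 3.3.1 is "Presence of active trigger point in upper trapezius". The same list requires mechanical cervical pain of under three months' duration and a VAS score above 3 and below 8 "for neck and cervical regions in the last 30 days". Section 3.3.2 excludes "Presence of whiplash injury or other cervical pathologies such as herniated disc", among other conditions.
- **Definition.** Section 1 states that "active trigger points have spontaneous local pain and referred pain away from the trigger point spot". A latent point hurts only under mechanical pressure, which can "evoke local and/or referred pain without spontaneous pain".
- **Identification.** Section 3.4 says: "The active trigger point in upper trapezius will be localized through manual palpation". It then applies cited "criteria, featuring 3 of 4 items". In short, the items are a taut band on palpation, a hypersensitive spot within it, pain the woman recognises as her own, and painful restriction at full stretch.
- **Screening.** Section 3.3 sends interested women to an "evaluation selection where it will be identified if the participant fits the inclusion criteria".

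**The concern.** Section 1 allows pressure to provoke referred pain from a latent point as well as an active one. By the document's own wording, spontaneous pain is therefore the feature that tells them apart. Yet all four items in section 3.4 are obtained by examination, through palpation or stretch, and none records pain that arises without provocation. Familiar-pain recognition comes nearest, but any three items suffice, so a point can qualify on the other three.

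It can thus look as if the trial requires one kind of trigger point and screens for either kind. The marked point is where the needle is aimed in two groups, the reference for the 1.5 cm offset in the third, and the site of the laser and the algometer. If some enrolled women had only latent points, the treated population would differ from the one described, and differences in VAS and NDI might be smaller than in women with active points only.

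**Working it through.** The plan states no figure on this point, so the check is to set the sections side by side.

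**Step 1: does the 3-of-4 rule separate active from latent?** The separator in section 1 is spontaneous pain.

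| Item in section 3.4 | How it is obtained | Records spontaneous pain? |
|---|---|---|
| 1. Taut band | Palpation | No |
| 2. Hypersensitive spot in the band | Palpation | No |
| 3. Familiar pain recognised | Woman's report on examination | No, though it links the point to her own complaint |
| 4. Painful restriction at full stretch | Stretch | No |

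None of the four does, and items 1, 2 and 4 together meet the threshold without item 3. Taken alone, the rule does not establish active status. This part of the concern is correct.

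**Step 2: is the rule meant to stand alone?** No. Active status is its own criterion in section 3.3.1, and section 3.3 has every inclusion criterion checked at the selection evaluation. Section 3.4 refers to the active point as the thing being located and gives the features by which it is recognised. A woman whose point meets three items but is judged latent still fails section 3.3.1. The sections fit together and do not contradict each other.

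**Step 3: what else constrains enrolment?** Every woman must have recent mechanical cervical pain and a VAS score above 3 and below 8 over the last 30 days, and other cervical pathologies are excluded. A woman with no symptoms and a point that hurts only when pressed is therefore not eligible. These criteria describe the region and not the marked point, so they narrow the risk without removing it. The remaining case is a woman with neck pain whose marked point is not its source.

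**Step 4: what could this do to the comparison?** The criteria are the same for all three groups, so any latent points are expected equally in each arm under randomisation. That rules out a systematic difference between groups from this source.

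Dilution remains possible. Let *q* be the share of women with latent points and *r* the fraction of the full between-group difference that they retain. The expected difference is then multiplied by

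1 − *q*(1 − *r*).

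The factor is 1 (no loss) if *q* = 0 or *r* = 1, and falls to 1 − *q* if *r* = 0. The documents give neither *q* nor *r*. They also give no target effect or standard deviation, since section 3.3 describes the 20 per group as a convenience sample based on reviews. Any power figure would only reflect the values chosen for these inputs.

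**Step 5: is the confirming step certainly absent?** Only from the text available. The document ends with an appendix heading and no content beneath it, and an evaluation form could have been there. The statement should be limited to the sections that can be read.

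**The case for a change.** The strongest case for acting is that an eligibility criterion should say how it is met. Active status comes first in the list, the document gives a definition that turns on spontaneous pain, and no visible section says that anyone asks about it. A later report that all 60 women had active points could not be traced to a recorded observation. One sentence in section 3.3.1 or 3.4, with a few boxes on the evaluation form, would settle it at almost no cost. If familiar-pain recognition is what the investigators rely on, they need only say so.

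The textual observation stands, and the sentence would help anyone reading the trial report. But the remedy asks only that an existing step be described. It does not alter who is eligible, how many are recruited, what is measured or how the data are analysed. It also leaves the choice of observation to the investigators, who already have to make that judgement to apply section 3.3.1. The cited sources for the identification criteria and for the active/latent distinction may say more, but they are not available here and nothing in this conclusion relies on them.

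**Conclusion.** No change to the plan is needed. The four items in section 3.4 do not by themselves distinguish active from latent points, and the visible text does not name the observation that does. This is a gap in description that a clinician applying section 3.3.1 fills at screening, with the woman's pain history and the palpation findings both to hand.

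There is no internal contradiction and no between-group bias. No effect on PPT or EMG has been shown. Some dilution of VAS and NDI differences is possible in principle, but the documents do not allow its size to be estimated.

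The conclusion rests on two assumptions: that the active criterion is applied in addition to the 3-of-4 rule, as the separate listing in section 3.3.1 implies, and that the same screening is used whatever group a woman is later assigned to. Stating in the trial report how active status was accepted, and which items were met, would be good practice.

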3.5. Intervention Protocols

3.5.1. Dry needling protocol

The Dry Needling (DN) protocol will be performed in one session. It will be used acupuncture needles, individually packaged and sterilized, with 0.25 mm of thickness and 0.40 mm of length. Before the intervention, the skin will be clean with 70% alcohol. The therapist, then, will perform the grip in upper trapezius on the site of one of the two previously marked locations, according to the subject group allocation, and will insert the needle in the skin with help of a guide tube and will deepen the needle approximately 10 to 15 mm inside the trigger point (31).

The needle will be moved up and down as in the “fast-in and fast-out” technique described by Hong (18). The movement will be repeated during 30 seconds in a cadence of approximately 1 Hz (31). Once the study of Perreault, Dunning & Butts (32), in 2017, demonstrated that there is no need to seek the local twitch response to the DN have an effect, we do not have the aim to seek such response to the stimulus. The protocol will be the same for the groups that will receive the application directly on the trigger point and for the group that will receive the application away from the trigger point.

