3.5.2. Photobiomodulation protocol

The photobiomodulation protocol will be performed using an equipment from Ibramed Equipamentos Médicos® of Aluminized Gallium Arsenide (AsGaAl) laser diode, with a wavelength of 830 nm, fluency of 20 J/cm², 30 mW, beam area of 0.116 cm², energy of 2,3 J

per point, continuous beam (22). The low-level laser therapy (LLLT) will be applied for 30 seconds at one point on the trigger point in upper trapezius, right after the dry needling application.

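### As written, the therapist may know the laser state before needling, so a hand-delivered needling difference between On and Off could be read as a laser effect

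*Combined protocol and SAP*

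**What the plan says.** Section 3.1 defines three groups, each by a needle site and a laser state:

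- "Group On: application of dry needling and LLLT turned on directly on the trigger point"
- Off: needled at the same site as On, but with the laser inactive
- Control: "application of dry needling and LLLT turned off away from the trigger point"

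Section 3.4 has two marks made on every participant: the trigger point, and a point 1.5 cm medial to it. Section 3.5.1 has the therapist needle "one of the two previously marked locations, according to the subject group allocation". The therapist "will deepen the needle approximately 10 to 15 mm inside the trigger point", and moves the needle for 30 seconds "in a cadence of approximately 1 Hz". The same section specifies a guide tube, says that a local twitch response is not sought, and states that the needling protocol is common to the on-point and off-point groups. Section 3.5.2 places the laser "right after the dry needling application".

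The abstract gives the hypothesis: "The hypothesis is that the association of the purposed interventions will have greater effects than only the dry needling intervention". The end of the Introduction repeats that aim and adds a comparison with placebo.

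The protocol does not say who holds the allocation, how it is concealed, who operates the laser, or when its state becomes known. It describes no masking of the therapist and no record of how the needling was delivered.

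**The concern.** The needling step needs one piece of information: which of the two marks to use. The group label carries a second piece, the laser state. A therapist who works from the label has both before the needle goes in.

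This matters most for On versus Off. These groups are meant to receive the same needling at the same site, so that the laser is the only difference between them. If knowing that active laser will or will not follow changes how the needle is handled, any resulting change in outcome becomes part of the On minus Off difference. The two-way ANOVA in section 3.6 has no term for delivery that could separate the two. A larger sample would estimate the mixture more precisely without removing the bias. The issue lies in delivery of treatment, so masking whoever takes the outcome measurements would not resolve it.

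**Working it through.** **Step 1: what the therapist needs and what the label reveals.** Setting section 3.1 beside section 3.5.1:

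| Group | Needle site | Laser | Needed to needle | Carried by the label |
|---|---|---|---|---|
| On | trigger point | on | trigger-point mark | mark and laser on |
| Off | trigger point | off | trigger-point mark | mark and laser off |
| Control | 1.5 cm away | off | second mark | mark and laser off |

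On and Off need the same needling instruction. Only the laser state tells them apart, and section 3.5.2 does not call for it until the needling is over. Withholding it until then is therefore feasible.

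**Step 2: room for needling to vary.** Duration (30 seconds), guide tube, needle type and the decision not to seek a twitch are fixed. Depth is a range of 15 − 10 = 5 mm, itself approximate, and cadence is approximate. Both are set by hand.

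**Step 3: what a shift would do.** The protocol gives no effect size, SD or power. Its only relevant figure is the sample size in section 3.3, 3 × 20 = 60, which agrees with the stated total but is a convenience sample. What follows is an illustration, not a reproduction of a plan figure.

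Inputs:
- n = 20 per group (section 3.3).
- Significance level 0.05 (section 3.6). Sidedness is not stated, so two-sided is assumed.
- True laser effect zero (assumed).
- Needling shift b in favour of On, in SDs of the outcome (assumed: 0 to 0.5).
- A two-sample t-test at one time point stands in for the two-way ANOVA, because the within-subject correlation is not given.

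Degrees of freedom are 2 × 20 − 2 = 38 and the critical value is 2.024. The standard error of the difference is √(2/20) = 0.316 SD. The test statistic is noncentral t with noncentrality b / 0.316 = 3.162b.

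| b (SD) | Noncentrality | Significant in favour of On | Significant in either direction |
|---|---|---|---|
| 0 | 0 | 2.5% | 5.0% |
| 0.1 | 0.316 | 4.9% | 6.1% |
| 0.2 | 0.632 | 9.0% | 9.5% |
| 0.3 | 0.949 | 15.0% | 15.2% |
| 0.5 | 1.581 | 33.8% | 33.8% |

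A normal approximation for the third column gives 2.5%, 5.0%, 9.2%, 15.6% and 35.2%, in reasonable agreement. If the shift favoured Off, the last column would be unchanged and the false results would point the other way. With a real laser effect, such a shift would hide part of it.

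The 95% confidence interval for On minus Off has half-width 2.024 × 0.316 = 0.64 SD. A shift of 0.2 to 0.3 SD lies well inside that, and the data could not distinguish it from a laser effect.

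**The case against.** The strongest objection is that the therapist's knowledge is inferred. The sentence in section 3.5.1 says what determines the site; it does not say what the therapist is told. A site-only instruction derived from the allocation would fit it equally well. This stands. A reader might infer that the therapist does know the laser state, but the documents support only that the therapist may know it, because the label includes it and nothing described withholds it. If a site-only instruction was always intended, the fix simply writes it down.

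Second, the needling is more standardised than the two approximate quantities suggest. Fixing the duration, using a guide tube, not seeking a twitch and stating a common protocol all narrow the room for difference. This also stands. It does not close the gap, since depth and exact cadence stay in the therapist's hand and no delivery record would show whether the common protocol was kept.

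Third, the shifts are assumptions of unknown size and direction. At 0.1 SD the rejection rate is 6.1%, close to nominal, and a change in depth or stroke rate need not change the outcome at all. That is correct, and the table should not be read as an estimate of this trial's error rate.

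Fourth, the protocol also describes no masking of participants or assessors, while pain, disability and pressure threshold all depend on participant report. That may well be a larger route to bias. It is a separate one, and does not remove a route that can be closed so cheaply.

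**Conclusion.** The concern holds as a risk that the written procedure leaves open. The therapist may know the laser state before needling, and a needling difference arising from that knowledge would be confounded with the laser effect in the contrast that carries the hypothesis. The conclusion rests on the three-level group label, the absence of any described masking, and the hand-delivered elements of needling.

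No size or direction can be derived from the documents. Under the stated assumptions, rejection with no laser effect runs from 5% (no shift) through 6%, 9.5% and 15% to 34% (shift of 0.5 SD).

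A reader might go further and conclude that needling will differ between On and Off, or that the comparison is biased towards the laser. The documents support neither: they report no delivery data, and a therapist could equally compensate in Off. The change is worth making because the threat falls on the main comparison and costs little to remove.

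**What to change.** In sections 3.5.1 and 3.5.2, disclose the allocation in two steps, by the same procedure in all three groups:

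1. Once both marks and all baseline readings are complete, give the therapist a site-only instruction naming which of the two marks to needle.
2. Disclose the laser state only after the needle has been withdrawn.

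Two sealed envelopes per participant, opened in sequence, would be one way to do this. On and Off participants would then carry identical first instructions.

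This removes needling differences caused by knowing the laser state in On versus Off; from this source alone, b = 0 and the illustrative rejection rate returns to 5%. It has limits. Random variation in needling remains. The operator is not masked during the laser step or afterwards. The needle site that separates Control stays visible to the therapist, so Off versus Control gains nothing.

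The cost is preparing a two-part concealed allocation, which is new work because the protocol describes no concealment method now, and a few seconds between needle and laser, equal in all groups. Sample size, visits, number of staff and treatment settings do not change. If needling has already been carried out, the report should say whether the therapist knew the laser state beforehand and present On versus Off with that limitation.
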